8.2.2 Patient Eligibility

8.2.2.1 Inclusion Criteria

Women exposed to Repatha during pregnancy and their infants through the first year of life who consent to provide their information to Amgen.

8.2.2.2 Exclusion Criteria

None.

8.2.3 Matching

Not applicable.

8.2.4 Baseline Period

This study has no formal baseline period. Pregnant women exposed to Repatha for any number of days, at any dose, and at any time from up to 90 days prior to the LMP and up to and including the end of pregnancy will be identified through Amgen's Global Safety Database and other post marketing sources which include: spontaneous (including regulatory authority and literature), solicited (ie, patient support programs and market research), and postmarketing non-interventional studies.

8.2.5 Study Follow-up

If pregnant women consent, they will be followed from the later date of the first day of their LMP or the date of their exposure to Repatha (index date) through the pregnancy and birth. A postpartum follow-up will occur approximately 6 to 8 weeks after delivery. Additional follow-up will occur when the infant is 6 and 12 months of age.

8.3 Variables

8.3.1 Exposure Assessment

The period defining exposure to Repatha during pregnancy will be any number of days, at any dose, and at any time from 90 days prior to the first day of the LMP up to and including the end of pregnancy. Identification of pregnancy will be via postmarketed reporting through Amgen's Global Safety Database.

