6.1 Diseases and Therapeutic Area

A serine protease expressed predominantly in the liver, kidney, and intestine (Seidah et al, 2003), proprotein convertase subtilisin kexin type 9 (PCSK9), plays an important role in the recycling and regulation of the LDL receptor (Horton et al, 2007; Brown and Goldstein, 2006). PCSK9 acts via direct binding to the LDL receptor, resulting in post-translational down-regulation of receptor expression on the hepatic cell surface. This in turn leads to increased levels of circulating LDL-C. Repatha is a fully human monoclonal IgG2 that binds specifically to human PCSK9 and prevents the interaction of PCSK9 with the LDL receptor, thus lowering plasma LDL-C levels.

Based on modality, mechanism of action, published human data, and nonclinical studies, safety issues during pregnancy are not expected with Repatha exposure. As a therapeutic monoclonal antibody, placental transfer during organogenesis in humans is likely to be low (DeSesso et al, 2012; ICH, 2009). Further, the conceptus derives at least 80% of its cholesterol needs from endogenous synthesis rather than from the maternal circulation (Bartels et al, 2012; Woollett, 2005). Independence from maternal sterol status indicates that normal fetal development would not be expected to be affected by the cholesterol lowering properties of Repatha which are independent of effects on cholesterol synthesis. Across multiple species including humans, the rates of cholesterol synthesis in the fetus are much greater than in the adult (Dietschy et al, 1993). Consistent with this, low maternal cholesterol is not causally associated with adverse birth outcomes. Whether mediated by dietary intervention or by genetic mutations, normal embryo-fetal development has been observed in children born to mothers with low cholesterol throughout pregnancy (Homanics et al, 1993; McMurry et al, 1981; Connor et al, 1978).

Moreover, in animal and reproduction studies, there were no effects on pregnancy or neonatal/infant development when monkeys were subcutaneously administered Repatha

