8.3.2 Outcome Assessment

Pregnancy outcomes include the number of women reporting pregnancy or maternal complications, as well as, the number reporting:

- Live full-term births
- Spontaneous abortion defined as non-deliberate fetal death which occurs prior to 20 completed weeks post-LMP
- Elective abortion defined as deliberate termination of pregnancy at any time in gestation
- Fetal death/Stillbirth defined as non-deliberate fetal death anytime in gestation at or after 20 completed weeks post-LMP
- Premature delivery defined as live birth prior to 37 weeks gestation as counted from LMP (eg, ultrasound adjusted date or Ballard's score)

Outcomes related to pregnancy and maternal complications will be assessed with a Pregnancy Questionnaire (a sample form included in [Appendix C](#)). Outcomes for live births will be assessed with a Post Due Date Questionnaire (a sample form included in [Appendix D](#)) from the Amgen Global Safety Database.

The number of infants with adverse events including complications, medical problems or congenital anomalies at birth will be assessed with a Post Due Date Questionnaire (a sample form included in [Appendix D](#)) from the Amgen Global Safety Database.

Major malformations or birth defects are defined as abnormalities incompatible with life or requiring medical/ surgical intervention. The term minor birth defect generally refers to minor physical anomalies with less clinical importance that represent deviations from what is considered normal and do not have obvious medical, surgical, or cosmetic consequences. Major birth defects identified up to 1 year of age by the mother or the healthcare provider will be included in the primary analysis. Major structural birth defects may be reported by the mother, a family member or her or her child's HCP via medical records. If a major malformation is reported the medical record will be adjudicated by a physician with expertise in teratology, pediatrics, and dysmorphology. Defects will be

classified using the Center for Disease Controls (CDC) criteria (CDC 2017.:
<https://www.cdc.gov/ncbddd/birthdefects/macdp.html>).

Infant outcomes are the number of cases reporting adverse events at 6 months and 12 months and may include whether they have not followed growth curves or met development milestones as expected for chronological age. These outcomes will be assessed with an Infant Questionnaire (a sample form included in [Appendix E](#)).

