8.7.2.3.3 Analysis of the Primary, Secondary, and Exploratory Endpoint(s)

All analyses will be descriptive. These cases constitute a case series, thus line listings of pregnancy and maternal complications, pregnancy outcomes, infant outcomes and adverse events will be summarized along with tabulations of the numbers and frequencies of events by category of report: numbers who did not provide consent for follow-up, timing of exposure (first, second, or third trimester), and indication for use of the medication. Collection of exposure and outcome information in this group provides additional evidence on the safety of Repatha use during pregnancy. The denominator is the number of pregnant women exposed to Repatha during pregnancy and the numerator is the number with the outcome.

The proportion of infants with adverse events including complications, medical problems or congenital anomalies at birth will be assessed in infants of women exposed to Repatha during pregnancy with corresponding 95% confidence intervals. The proportion of infants with adverse events at 6 months and 12 months of age will be assessed. All adverse events among mothers who have received Repatha at any time during the pregnancy will be summarized including the proportion with pregnancy and maternal complications. To assess events in the developing fetus and neonate in women exposed to Repatha during pregnancy, the proportion of pregnancies resulting in spontaneous abortions, elective abortions, fetal death/ stillbirths and premature delivery will be presented, along with corresponding 95% confidence.

If the available safety information relevant to exposure during pregnancy represents a safety signal, the signal will be further evaluated through the Amgen safety governance structure and, if deemed necessary, escalated for consideration of changes to the Reference Safety Information (eg, USPI) as well as other forms of risk communication (eg, Dear Healthcare Provider Letters).

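### Major birth defects are counted over all infants exposed at any time up to the end of pregnancy, so infants first exposed after organ formation enter the estimate and dilute any effect of early exposure.

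*Protocol*

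**What the plan says.** Only the protocol is at hand. It fixes the following.

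- **Exposure (8.3.1).** Any number of days and any dose, "at any time from 90 days prior to the first day of the LMP up to and including the end of pregnancy". The abstract and section 8.2.4 use the same window.
- **Eligibility (8.2.2).** The inclusion criterion is "Women exposed to Repatha during pregnancy and their infants through the first year of life who consent to provide their information to Amgen". There are no exclusion criteria, so nothing limits when in pregnancy the first dose may fall.
- **Index date (8.2.5).** Follow-up runs from "the later date of the first day of their LMP or the date of their exposure to Repatha (index date"). A first dose well after LMP is thus foreseen.
- **Major defects (8.3.2).** "Major birth defects identified up to 1 year of age by the mother or the healthcare provider will be included in the primary analysis". Nothing requires the exposure to precede the formation of the defect. Section 8.7.5.1.1 confirms that a birth-defect frequency belongs to the primary analysis, because defects found in fetal losses are set apart from it.
- **Analysis (8.7.2.3.3).** The denominator is all women exposed during pregnancy. The proportion of infants with adverse events at birth, a composite that includes congenital anomalies, "will be assessed in infants of women exposed to Repatha during pregnancy with corresponding 95% confidence intervals".
- **Timing.** Section 8.7.2.3.3 plans tabulations of event numbers and frequencies by first, second or third trimester of exposure. The abstract adds a pre-LMP category. Sections 8.7.2.4.1 and 8.7.2.4.2 declare subgroup and stratified analyses not applicable.
- **Checklist (Appendix B, items 5.3 and 5.5).** Both answer yes to exposure being categorised, by time windows and by mechanism and pharmacokinetics, and cite 8.3.1. That section contains one undivided window.

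**The concern.** One exposure definition serves every outcome. It suits maternal, neonatal and first-year events, which can follow a dose at any stage. It does not suit major structural defects, which arise while the organs form. An infant first exposed in the third trimester can have such a defect, but the defect is then older than the infant's own index date. Counting that infant has two effects: a defect that precedes exposure enters the numerator, and an infant whose structural-defect risk the drug could not have changed enters the denominator.

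If early exposure raises the risk, each late starter pulls the pooled proportion toward the background. Section 8.7.2.3.3 lets the safety information from this study feed signal evaluation and possible labelling changes, so what the defect proportion represents matters.

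**Working it through.** **Plan's own figure.** None to reproduce. The protocol states no study size (8.5), no expected defect frequency and no distribution of exposure timing. Everything below except the structure of the estimate is an assumption for illustration.

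**Inputs.**
- From the protocol: estimate pooled over all timings (8.3.1, 8.3.2, 8.7.2.3.3); 95% confidence intervals.
- Assumed: background risk p0 = 3%; true risk ratio RR = 2 for early exposure, hence early risk 6%; share s first exposed after organ formation = 10%, 25%, 40%; total infants N = 50 to 400. Late starters are taken to carry the background risk.

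**Step 1, dilution.** p_pooled = (1 − s)·RR·p0 + s·p0, so p_pooled − p0 = (1 − s)·(RR·p0 − p0). The share of the excess that is kept is 1 − s, whatever p0 and RR are.

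- s = 10%: 0.90 × 6% + 0.10 × 3% = 5.7%; ratio 5.7/3 = 1.9
- s = 25%: 0.75 × 6% + 0.25 × 3% = 5.25%; ratio 1.75
- s = 40%: 0.60 × 6% + 0.40 × 3% = 4.8%; ratio 1.6

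The proportion among early-exposed infants is 6% (ratio 2.0) at every s.

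**Step 2, defects that precede exposure.** Their share of all counted defects is s·p0 / p_pooled: 0.3/5.7 = 5%, 0.75/5.25 = 14% and 1.2/4.8 = 25% for the three values of s.

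**Step 3, does restriction help detection?** Probability that the exact lower 95% limit exceeds 3%, from the binomial distribution with upper tail at most 0.025. This is a yardstick only; the protocol plans no such criterion.

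| N | s | Pooled | Early-exposed only |
|---|---|---|---|
| 400 | 10% | 0.757 | 0.749 (n = 360) |
| 400 | 25% | 0.62 | 0.72 (n = 300) |
| 400 | 40% | 0.46 | 0.58 (n = 240) |
| 200 | 25% | 0.36 | 0.41 (n = 150) |
| 200 | 40% | 0.25 | 0.29 (n = 120) |
| 100 | 25% | 0.155 | 0.163 (n = 75) |
| 50 | 10% | 0.15 | 0.13 (n = 45) |
| 50 | 25% | 0.12 | 0.08 (n = 38) |

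Restriction gains when late starters are common and the series is large. It gains nothing at N = 400 with s = 10%, and it loses at N = 50 with s = 10% or 25%. The discreteness of the exact test moves the small-sample figures about. The dilution in step 1 does not depend on N.

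**Step 4, does the timing tabulation remove the problem?** It would show events by trimester, but three things are lacking. No confidence interval is stated for its rows. It does not separate a first exposure in a trimester from continued exposure, so a woman treated throughout and a third-trimester starter can both appear under the third trimester. And section 8.7.2.3.3 drops the pre-LMP category that the abstract lists, although 8.3.1 counts those women as exposed.

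**The case against.** The strongest reply is that timing is already separated: the trimester tabulation is planned, and Appendix C collects start and stop dates and the weeks of pregnancy in which the drug was taken. Which row carries an interval could be left to the statistical analysis plan. This stands in part. A reader who inferred that the protocol ignores timing would be wrong. But the protocol itself states the pooled denominator and puts major defects into the primary analysis on that basis, and the tabulation has the gaps in step 4.

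Four further limits stand.

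- The sentence with the interval in 8.7.2.3.3 concerns the broad at-birth composite. One might infer that the protocol attaches an interval to a major-defect proportion; it does not say so. For the composite, late exposure is relevant and restriction would be wrong.
- Section 6.1 might be read as naming organogenesis as the risk window. It says only that "placental transfer during organogenesis in humans is likely to be low", which is an argument for reassurance. The relevance of early exposure rests on when structural defects form, not on that sentence.
- It is tempting to call the pooled figure falsely reassuring. The study is descriptive, with no comparator, background rate or hypothesis, so the documents support dilution of any early excess, not a wrong conclusion.
- Restricting to doses from LMP to the end of the first trimester, with a row only for later starters, would leave women exposed solely in the 90 days before LMP without a row of their own.

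**Conclusion.** The point holds for major structural defects. As written, their proportion covers infants exposed at any time, includes defects that precede a late first dose, and keeps only 1 − s of any excess from early exposure. That direction follows from the definitions, given that late starters carry the background risk for structural defects and that early exposure raises it; with no early effect, nothing is diluted.

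The size cannot be set from the protocol. At s = 10% an assumed ratio of 2.0 becomes 1.9; at s = 40% it becomes 1.6. If most women conceive while on treatment, the loss is small. A gain in the chance of detecting an excess is not assured, so the case rests on a correctly defined estimate rather than on power. The planned tabulation by timing mitigates the problem but does not remove it.

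**What to change.** In sections 8.3.2 and 8.7.2.3.3, for major structural defects only:

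1. Make the main proportion, with its 95% confidence interval, the one among infants whose mothers were exposed in a stated window covering the first trimester.
2. State whether exposure only in the 90 days before LMP belongs to that window or has its own row.
3. Report infants first exposed in the second or third trimester in a separate row, outside the main numerator and denominator, and classify by first exposure so that continued use is not confused with a late start.
4. Keep the any-time proportion as supportive.

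Leave the any-time definition in place for the at-birth composite and for maternal, neonatal and first-year outcomes. Reconcile the timing categories of the abstract with those of 8.7.2.3.3, and bring checklist items 5.3 and 5.5 into line with what 8.3.1 contains.

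The cost is wording and a few table rows. Appendix C already asks for the dates; reports that lack them will need a row for unknown timing. The downside is a smaller denominator and a wider interval for the defect estimate.

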8.3.2 Outcome Assessment

Pregnancy outcomes include the number of women reporting pregnancy or maternal complications, as well as, the number reporting:

- Live full-term births
- Spontaneous abortion defined as non-deliberate fetal death which occurs prior to 20 completed weeks post-LMP
- Elective abortion defined as deliberate termination of pregnancy at any time in gestation
- Fetal death/Stillbirth defined as non-deliberate fetal death anytime in gestation at or after 20 completed weeks post-LMP
- Premature delivery defined as live birth prior to 37 weeks gestation as counted from LMP (eg, ultrasound adjusted date or Ballard's score)

Outcomes related to pregnancy and maternal complications will be assessed with a Pregnancy Questionnaire (a sample form included in [Appendix C](#)). Outcomes for live births will be assessed with a Post Due Date Questionnaire (a sample form included in [Appendix D](#)) from the Amgen Global Safety Database.

The number of infants with adverse events including complications, medical problems or congenital anomalies at birth will be assessed with a Post Due Date Questionnaire (a sample form included in [Appendix D](#)) from the Amgen Global Safety Database.

Major malformations or birth defects are defined as abnormalities incompatible with life or requiring medical/ surgical intervention. The term minor birth defect generally refers to minor physical anomalies with less clinical importance that represent deviations from what is considered normal and do not have obvious medical, surgical, or cosmetic consequences. Major birth defects identified up to 1 year of age by the mother or the healthcare provider will be included in the primary analysis. Major structural birth defects may be reported by the mother, a family member or her or her child's HCP via medical records. If a major malformation is reported the medical record will be adjudicated by a physician with expertise in teratology, pediatrics, and dysmorphology. Defects will be

classified using the Center for Disease Controls (CDC) criteria (CDC 2017.:
<https://www.cdc.gov/ncbddd/birthdefects/macdp.html>).

Infant outcomes are the number of cases reporting adverse events at 6 months and 12 months and may include whether they have not followed growth curves or met development milestones as expected for chronological age. These outcomes will be assessed with an Infant Questionnaire (a sample form included in [Appendix E](#)).

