Appendix C. Initial Pregnancy Questionnaire – Mother

Safety Database #

INITIAL PREGNANCY QUESTIONNAIRE (MOTHER)

You may return completed form to Amgen Office Fax or Email:

[contact] Email: [contact]

Section 1 – Reporter Information

Reporter: Mother Health Care Professional Other _____ Parent exposed to product? Mother Father
 Name _____ Phone () _____ Fax () _____
 Email _____ Address _____ City _____
 State/Province _____ Zip/Postal Code _____ Country _____
 *Did the patient sign the Authorization for Release of Medical Information? Yes No

In the event your contact information changes, please provide a back-up contact (for example a close relative or friend who does not live with you) who we may reach in an effort to contact you.

Relationship to patient: _____
 Name _____ Phone () _____ Fax () _____
 Email _____ Address _____ City _____
 State/Province _____ Zip/Postal Code _____ Country _____

Section 2 – Mother Current Pregnancy Information

Mother's Initials: _____ Date of birth: (if permitted to provide by local laws) _____ Date of last menstrual period: _____
 Age: _____ years Day _____ Month _____ Year _____ Day _____ Month _____ Year _____
 Number of fetuses: _____ Estimated date of delivery: _____
 Day _____ Month _____ Year _____

Relevant Laboratory Tests & Procedures

Test Name	Test Date (dd/mm/yr)	Test Result

Section 3 – Mother Prenatal Medication History

Please list all medications (prescription and over-the-counter [include vitamins, herbal medications, etc.] and vaccines, taken by the mother within 3 months prior to or during pregnancy.

Amgen Product Used	Dose	Route (e.g. oral, subcutan.)	Frequency (e.g. daily, weekly)	Date Drug Started (dd/mm/yy)	Date Drug Stopped (dd/mm/yy)	Weeks of Pregnancy When Drug Taken (e.g. wk 28–wk 32)	Indication for Treatment
Resumed (if applicable)							

Amgen Product Lot Number _____ Lot Number Not Known

Safety Database #

List any other medications used within 3 months prior to or during the pregnancy

Medications/Drugs	Dose	Route (e.g. oral, subcutaneous)	Frequency (e.g. daily, weekly)	Date Drug Started (dd/mm/yy)	Date Drug Stopped (dd/mm/yy)	Indication for Treatment

Section 4 – Pregnancy Complication and Adverse Event Information

If the **mother** experienced any pregnancy complications (e.g. preeclampsia, gestational diabetes, placenta previa, etc.) please complete the following:

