6 TO 8 WEEKS POST DUE DATE QUESTIONNAIRE (MOTHER)

Section 1 – Reporter Information

Reporter: Mother Health Care Professional Other _____

Any change in the reporter contact information? Yes No If yes, please provide updated contact information:

Name _____ Phone () _____ Fax () _____

Email _____ Address _____ City _____

State/Province _____ Zip/Postal Code _____ Country _____

Section 2 – Mother Prenatal Medication History

Please provide any additional medication information for medicines used during your pregnancy not previously reported. For example, if you resumed or discontinued the Amgen Product or any other medications during the pregnancy (include vitamins, folic acid, herbal medications, and vaccines).

Medications/Drugs	Dose	Route (e.g. oral, subcutaneous)	Frequency (e.g. daily, weekly)	Date Drug Started (dd/mm/yy)	Date Drug Stopped (dd/mm/yy)	Indication for Treatment

Section 3 – Mother Pregnancy Complications and/or Adverse Event Information

Pregnancy Complication or Adverse Event (e.g. preeclampsia, gestation diabetes)	Date the Complication or Event Started (dd/mm/yy)	Date the Complication or Event Resolved (dd/mm/yr)	Outcome (for example: resolved, not resolved, unknown, other, etc.)

Amgen Proprietary - For Internal Use Only

6 to 8 Weeks Post Due Date Questionnaire (Mother)

Version 1. Effective: 16 September 2015

Page 1 of 2

Safety Database # [case_id]

6 TO 8 WEEKS POST DUE DATE QUESTIONNAIRE (MOTHER) *continued*

Section 4 – Mother Current Pregnancy Outcome (if applicable)

Date pregnancy ended: _____ Weeks of pregnancy at delivery (or if the outcome was a
Day Month Year loss of pregnancy): _____ weeks

Pregnancy Outcome (please check the appropriate box below)

- Live birth
 - Number of infants _____ (1: single, 2: twins, etc.)
(If multiple births: Please provide all information for each infant in the additional information text box below:)
- Pregnancy loss (miscarriage)
- Stillbirth
- Termination
 - Due to health issue (mother or baby)
 - For voluntary reason
 - Other (please specify): _____

If live birth: Gender: Male Female

Length: _____ cm/inches Birth weight: _____ gram/lb Head circumference: _____ cm/inches

Did the baby have any complications/medical problems/congenital anomalies (birth defects)? Yes No

If yes, please provide specific information below.

Additional Information on pregnancy outcome:

Section 5 – Reporter Signature

Signature of person completing questionnaire: _____ Date: _____

Please print name: _____

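### Section 8.3.2 assigns maternal complications to the initial questionnaire alone, although the post-due-date form also collects them and pregnancy losses; the source and the complication denominator need reconciling

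*Protocol*

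**What the plan says.** Protocol Section 8.3.2 is the place that links outcomes to instruments. For complications it says "Outcomes related to pregnancy and maternal complications will be assessed with a Pregnancy Questionnaire", pointing to Appendix C, whose title marks it as the initial questionnaire. For the second form, Appendix D, it says "Outcomes for live births will be assessed with a Post Due Date Questionnaire", and then "The number of infants with adverse events including complications, medical problems or congenital anomalies at birth will be assessed with a Post Due Date Questionnaire". It does not name Appendix D for maternal complications, miscarriage, termination or stillbirth.

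The forms are broader than this. Appendix D contains "Section 3 – Mother Pregnancy Complications and/or Adverse Event Information", a table with start date, resolution date and outcome. Its Section 4 offers live birth, miscarriage, stillbirth and termination, with the date and week at which the pregnancy ended. In Appendix C, Section 4 asks the respondent to fill in a table if the mother "experienced any pregnancy complications (e.g. preeclampsia, gestational diabetes, placenta previa, etc.) please complete the following". Section 7 of that form records the pregnancy outcome where it applies.

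Section 8.7.2.3.3, like the Abstract, sets the denominator as the exposed pregnant women and the numerator as those with the outcome.

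**The concern.** Pregnancy and maternal complications are the first primary objective (Section 7.1), and losses are among the primary pregnancy outcomes. When a pregnancy is still ongoing at first report, the initial form covers only the time up to its completion. Complications such as those given as examples on the form can begin later, and so can a loss.

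If an analyst follows 8.3.2 to the letter, later complications entered on Appendix D are not used for the complication count, and later losses have no form named for them beyond the initial one. The estimate would then depend partly on how early in pregnancy the report arrived. A second problem remains even if both forms are used: neither complication table lets the respondent say that there was none, so an empty table may mean no event or no answer.

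**Working it through.** The protocol gives no expected rate, event count or sample size on this point (Section 8.5 leaves the size to the number of reports). There is no figure to reproduce, so the check sets the text beside the forms.

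**Source of each outcome**

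| Outcome | Form named in 8.3.2 | Forms with a field for it |
|---|---|---|
| Pregnancy and maternal complications | Appendix C | Appendix C Section 4; Appendix D Section 3 |
| Live-birth outcomes, newborn problems | Appendix D | Appendix C Section 7; Appendix D Section 4 |
| Miscarriage, termination, stillbirth | Not named for Appendix D | Appendix C Section 7; Appendix D Section 4 |

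The sentence that assigns Appendix C can be read as covering complications only, or as covering pregnancy outcomes too. On the narrow reading losses have no named form. On the wide reading they are assigned to the initial form. Neither reading reaches Appendix D.

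**Do other sections settle it?** Only in part.
- Section 8.3.3.2 lists maternal conditions among the post-due-date variables, but as covariates. Section 8.3.3.1 puts the occurrence and dates of complications under pregnancy information, which repeats the split.
- Sections 8.2.5 and 8.4 plan contact after birth, Section 8.6 says the database is updated when more details arrive, and Section 8.7.3 takes outcomes as reported through the database. These show that the later data are held. They do not say that 8.3.2 is to be read as using them.

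**Can a negative be recorded?** Both forms give the newborn item an explicit Yes/No. Neither gives the maternal complication table one.

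**Effect on the proportion.** Let N be the exposed pregnancies, C those with a complication, and U those of the C whose complication is not recorded or not counted (only an early form, a table left blank, or a later table not used).
- Proportion sought among the N: C / N.
- Planned estimate: (C − U) / N.
- Shortfall: C/N − (C − U)/N = U / N, which is zero or positive.

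Taken alone, this mechanism can only lower the proportion. The documents give none of N, C or U, so its size cannot be derived. If both forms are pooled in practice, U shrinks to women without a later form and women with blank tables.

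**Opposing mechanism.** Section 8.7.2.2 expects women with adverse events to be likelier to report, and Section 8.7.5.1.1 expects women without complications to be likelier to decline consent or be lost. Both change who is among the N, and both push the proportion up. The two effects cannot be netted from the documents.

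**The case against.** The strongest reply is that the source is the whole case record. Follow-up continues after birth, the database is updated, it is said to hold abortions and stillbirths (Section 8.4), and Section 8.7.2.3.3 promises a summary of all maternal adverse events. On that view 8.3.2 is loose drafting. Much of this stands: the data are collected, and 8.3.2 nowhere says that Appendix D is restricted to live births and newborns.

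Three stronger readings are therefore tempting but unsupported.
- A reader might infer that later complications and losses are not captured. Appendix D Sections 3 and 4 show otherwise.
- A reader might put a size on the deficit. For example, assume a true proportion of 20% with 50% to 90% of complications starting after the first form: 20% × (1 − 0.5) = 10% and 20% × (1 − 0.9) = 2%. Those inputs are not in the protocol, and the result holds only if Appendix C were the sole source used and every woman completed it early in pregnancy.
- A reader might infer that the reported proportions will be too low overall. The protocol's own account of selective reporting points the other way.

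It can also be said that the endpoint counts cases that report a complication, so no recorded negative is needed, and that a form never returned is loss to follow-up, which Sections 8.7.5.1.1 and 8.7.7 acknowledge. This is fair for the count. It does not hold for the proportion, because the denominator treats every woman without a report as free of complications.

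**Conclusion.** The point holds as an inconsistency with a limited consequence. The source that 8.3.2 states for a primary outcome does not match the forms that collect it, and the passages must be reconciled. With the all-exposed denominator, early-only forms and blank tables count as no complication. This lowers the complication proportion by U / N, which the documents do not allow to be quantified.

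The conclusion assumes that some pregnancies are first reported while ongoing and that some of those lack later maternal information or leave the table empty. Pregnancies already over at first contact are not affected by form timing, though the blank-table problem applies to them too. The net direction, after selective reporting, is unknown. The matter should be corrected, but it does not invalidate the study.

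**What to change.** 1. Amend Section 8.3.2 along these lines: *Complications and every pregnancy outcome (live birth, spontaneous or elective abortion, stillbirth) are taken cumulatively from Appendix C, Appendix D and any follow-up with a healthcare provider.*
2. For prospective use, add above both complication tables: *Any pregnancy complication or adverse event? Yes / No / Unknown.*
3. Report the complication proportion among pregnancies with information obtained after the pregnancy ended, beside the planned proportion over all exposed pregnant women, and give the number in each denominator.

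The cost is protocol wording, one line on two existing forms and one extra column in a table. No new contact is needed because the post-birth follow-up is already planned. Section 11.1 requires the amendment to go to the FDA for agreement first. The assessed denominator is smaller and, by the protocol's own reasoning, may over-represent women with events, which is why both proportions should be shown. The tick box cannot repair retrospective reports, so for those the number with no information after the end of pregnancy should simply be stated.
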